## 9. INVESTIGATIONAL PLAN

### 9.1. Study Design

This is a phase 2 study that assesses the feasibility and efficacy of neoadjuvant immunotherapy in patients with previously untreated, surgically-resectable, solid tumor brain metastases. Histologic types are restricted to those known to extracranially respond to immunotherapy, and will include, but not be limited to, squamous non-small cell lung cancer (NSCLC), non-squamous NSCLC without known

ALK+, EGFR+, and ROS alterations, renal cell carcinoma (RCC), melanoma, and triple negative breast cancer (TNBC) that is PD-L1 positive, ovarian carcinoma, and urothelial carcinoma

Eligible participants will receive a single infusion of nivolumab at a dose of 3 mg/kg and ipilimumab at a dose of 1 mg/kg 7 days ( $\pm$ 3 days) prior to surgical resection of their metastases. Patients will then receive SRS 3 weeks ( $\pm$ 3 weeks) after surgery. Patients will be followed for 18 months after initiating study treatment. Up to 20 participants will be recruited and treated. Blood will be collected periodically during the study for correlative assessments as described in Section [12.7.5](#).

### **9.1.1. Definition of Dose-Limiting Toxicity (DLT)**

Not applicable.

#### **9.1.1.1. Non-hematologic:**

Not applicable.

#### **9.1.1.2. Hematologic:**

Not applicable.

#### **9.1.1.3. Other Considerations:**

Not applicable.

### **9.1.2. Dose Modification**

#### **9.1.2.1. Non-hematologic:**

Not applicable, only one dose of the study drug is given so there will be no intra-patient dose reduction. Similarly, the proposed doses of 3 mg/kg for nivolumab and 1 mg/kg for ipilimumab are recommended by the FDA.

#### **9.1.2.2. Hematologic:**

Not applicable, only one dose of the study drug is given so there will be no intra-patient dose reduction. Similarly, the proposed doses of 3 mg/kg for nivolumab and 1 mg/kg for ipilimumab are recommended by the FDA.

#### **9.1.2.3. Other considerations:**

Not applicable, only one dose of the study drug is given so there will be no intra-patient dose reduction. Similarly, the proposed doses of 3 mg/kg for nivolumab and 1 mg/kg for ipilimumab are recommended by the FDA.

### **9.1.3. Safety Considerations**

**Nivolumab safety:** The most common adverse reactions in cancer subjects in other clinical trials with nivolumab include fatigue; skin reactions including rash, itching, hives, redness, and dry skin; diarrhea; nausea; abdominal pain; decreased appetite; low red blood cells; fever; and joint pain or stiffness. Less common side effects include bowel inflammation, lever function blood test abnormalities, loss of color (pigment) from areas of skin, dry mouth, vomiting, weight loss, thyroid gland abnormalities, blood chemistry abnormalities, high blood uric acid level, lung inflammation (pneumonitis), cough, dizziness, headache, low white blood cells, chills, muscle soreness, muscle weakness, stiffness, muscle spasms, paralysis, pain in arms or legs, tingling in hands and feet, burning in hands and feet, numbness in hands and feet, shortness of breath, abnormal taste, flushing, high or low blood pressure, allergic reaction during or between study drug infusions, increased sensitivity of skin to sunlight, constipation, difficulty swallowing, heartburn, and low blood platelets. Rare, but potentially serious side effects include low blood oxygen level; acute lung injury or failure; collection of fluid around the lungs; inflammation of the appendix; increase in inflammatory blood proteins; adrenal gland abnormalities; pituitary gland inflammation; liver inflammation; changes in vision, inflammation of the eye, or bleeding into the eye; acute kidney injury or failure; abnormal blood cell production; inflammation of the mouth and lining of the digestive tract; swelling of the face, arms, or legs; inflammation of the pancreas; back pain; autoimmune disorders; chest discomfort; heart palpitations; inflammation of the heart or its lining; collection of fluid around the heart; increased blood sugar; dehydration; infections including sepsis, lung and skin infections; decreased movement of the intestines; disorientation; swelling of the optic disc; inflammation of the optic nerve; inflammation or loss of the lining of the brain and spinal cord; Drug Reaction with Eosinophilia and Systemic Symptoms (DRESS); central demyelination; abnormal brain function due to brain inflammation; rhabdomyolysis; polymyositis; and toxic epidermal necrolysis. Nivolumab can cause fetal harm when administered to pregnant women. Females of reproductive potential should use effective contraception while on treatment with nivolumab and for at least 5 months after the last dose. For additional information about nivolumab safety and adverse event management, please see Section 18.1.

**Ipilimumab safety:** Ipilimumab has been most frequently studied in subjects with advanced melanoma. Other studies have been conducted in subjects with prostate cancer and lung cancer. In previous studies in subjects with advanced melanoma, approximately 79-80% experienced a side effect from ipilimumab. Most were mild to moderate and resolved with proper medical treatment. Side effects that may occur during the infusion of ipilimumab include fever, hypotension, chills, flushing, nausea and/or vomiting. If an infusion reaction occurs, the infusion will be slowed or stopped until the symptoms have been treated. These symptoms can also occur hours after the completion of the infusion. The most common side effects of ipilimumab include diarrhea, fatigue, skin itchiness, skin rash, nausea, fever, decreased appetite, vomiting, colitis,

abdominal pain, headache, constipation. Less common side effects include chills, weakness, muscle pain, and redness of skin. Rare side effects (in less than 1% of subjects) include tumor lysis syndrome, which can result in elevation in certain blood levels (for example, uric acid, phosphorous, potassium) can cause the kidneys to shut down, the heart to function irregularly (for example, an irregular heartbeat), shortness of breath, and loss of consciousness.

Ipilimumab can cause side effects due to the immune system attacking normal cells, called immune-related adverse events or IRAEs. In previous studies in subjects with advanced melanoma, 72-76% of treated subjects developed an IRAE of any grade of severity. About 25-37% of subjects had a severe IRAE. These IRAEs have usually been controlled by stopping ipilimumab temporarily or permanently and if needed, with medications, including steroids (medications that are used to decrease inflammation).

For additional information about ipilimumab safety and adverse event management, please see Section [18.2](#).

**Surgical Complications:** The surgical resection carries a risk for cerebrospinal fluid leak, infection, hemorrhage, loss of neurologic function, non-neurologic complications, and death. These risks depend primarily on the preoperative condition of the patient, the size and location of the tumor and associated diseases. The potential risk for the patient will be discussed in detail with the patient and family.

**Stereotactic radiosurgery (SRS):** Side effects resulting from complications of SRS include tiredness and fatigue, headache, nausea, vomiting, reddening of the skin of the scalp, memory or neurological problems (rare), and late development of a second cancer (rare).

**Anesthesia:** Patients undergoing general anesthesia may be subjected to associated risks including pneumothorax, pneumonia, airway injury, hypotension, myocardial infarction, stroke, hepatic and renal injury and death.

**Peritumoral Inflammation and Increased Intracranial Pressure:** Peritumoral inflammation may be secondary to the disease process itself, the surgical procedure, necrosis from radiation, or inflammation due to immune infiltration of the brain or destruction of tumor cells. Symptoms may include, but are not limited to, severe headache, confusion, lethargy, unresponsiveness, coma, or focal neurological deficits. Patients will be monitored throughout the course of the study for peritumoral inflammation and upon any signs or symptoms of cerebral edema, may have their steroid doses increased or receive treatment with an antiangiogenic agent, osmotic diuretic, or surgical decompression. Edema that fails to respond to aggressive therapy may lead to permanent neurological impairment. The risks will be discussed with the subject and the subject's family.

Risk of Phlebotomy: Drawing blood or inserting an intravenous catheter into an arm vein may result in bruising or swelling in the area of the insertion, bleeding at the site of the needle puncture, light headedness, fainting and very rarely, local infection, which may be severe. These risks are reduced by the fact that the blood will be drawn by a qualified physician, nurse or phlebotomist (a professional trained to draw blood).

Risks of MRIs: Risks and/or discomforts associated with MRI scans include anxiety produced from being in a tight, enclosed space (claustrophobia). In addition, the machine operates using a large and powerful magnet, which attracts certain metals. Therefore, people with these metals in their bodies (specifically pacemakers, infusion pumps, metal aneurysm clips, metal prostheses, joints, rods or plates) will be excluded from the study. Patients will also be checked to make sure that they do not bring any metal objects into the MRI facility. Dental fillings are less affected by the magnetic fields generated and are therefore permitted. Patients will be asked to let the physicians conducting this study know of any metal in their bodies other than dental fillings.

Unknown Risks: The overall risk classification of this research is unknown.

#### **9.1.4. Missed Doses**

Not applicable as there is only one dose of the study agents given.

#### **9.1.5. Concomitant Medications**

##### **9.1.5.1. Steroids**

Corticosteroids should be used at the lowest dose to control symptoms of edema and mass effect, and discontinued, if possible. Use of corticosteroids should be recorded in the electronic research database (see Section 16.5). Every effort should be made to keep the dose of steroids at or lower than an equivalent of 4 mg daily of dexamethasone.

##### **9.1.5.2. Anticonvulsants**

Anticonvulsants drugs should be used or continued, if indicated. Use of such anticonvulsants should be recorded in the electronic research database.

##### **9.1.5.3. Growth Factors**

Routine use of growth factors (i.e. G-CSF, GM-CSF, and erythropoietin) is not permitted. However, therapeutic use of G-CSF in patients with serious neutropenic conditions, such as sepsis, may be used at the investigator's discretion. Use of such growth factors should be recorded in the electronic research database (see Section 16.5).

##### **9.1.5.4. Anti-emetics**

The use of anti-emetics will be at the investigator's discretion. Use of anti-emetics should be recorded in the electronic research database (see Section [16.5](#)).

#### **9.1.5.5. Proton Pump Inhibitors**

The use of proton pump inhibitors (PPI) (e.g. rabeprazole, omeprazole, pantoprazole, lansoprazole or esomeprazole) is allowed on this study and should be recorded in the electronic research database (see Section [16.5](#)).

#### **9.1.5.6. *Pneumocystis jiroveci* pneumonia (PJP) prophylaxis**

The use of medication (i.e., Bactrim) for PJP prophylaxis in patients on chronic steroids is recommended, but is at the investigator's discretion.

#### **9.1.5.7. Neurosurgical Procedures**

If a neurosurgical procedure is required for a reason other than tumor progression (i.e., the onset of hydrocephalus), these procedures should be documented, but will not constitute criteria for declaring the patient "off therapy."

### **9.1.6. Study Drug Blinding**

Not applicable.

### **9.1.7. Randomization**

As of 03/19/2021, randomization was removed from the study when a control arm without neoadjuvant nivolumab and ipilimumab was removed from the study design. See details in Section 15.1.

[figure not shown]
## **9.2. Rationale for Selection of Dose, Regimen, and Treatment Duration**

Both nivolumab and ipilimumab will be dosed at the FDA recommended dosing levels of 3 mg/kg and 1 mg/kg for combination therapy, respectively. Nivolumab and ipilimumab infusions will occur in the neoadjuvant setting, prior to surgery, with the expectation that neoadjuvant dosing will result in a more robust immune response than adjuvant dosing, as was seen in a study in GBM patients [\[16\]](#).

### **9.3. Rationale for Correlative Studies**

Due to the nature of their activity, checkpoint inhibitors like nivolumab and ipilimumab inherently alter the activity of the immune system. Inhibition of CTLA-4 and PD-1 on T cells using monoclonal antibodies (like ipilimumab and nivolumab) results in increased T-cell proliferation [\[17\]](#), and could serve as a surrogate marker

for therapeutic efficacy. It is important, therefore, to understand how T cells, both in the periphery and intratumoral, are affected by ipilimumab and nivolumab. In a study involving neoadjuvant administration of pembrolizumab in patients with recurrent GBM, tumor interferon- $\gamma$ -related gene expression was altered by neoadjuvant immunotherapy (Figure 3). Neoadjuvant treatment with pembrolizumab resulted in increased gene expression in a panel of 16 genes related to interferon- $\gamma$  expression for 9/14 tumors. Markedly, tumors that did not receive neoadjuvant pembrolizumab showed decreased gene expression for 10/14 tumors.

**Figure 3: Neoadjuvant immunotherapy alters intratumoral interferon- $\gamma$ -related gene expression.** The letter 'A' represents a tumor treated in the neoadjuvant setting. The letter 'B' represents a tumor treated in the adjuvant setting. The majority (10/14) of patients treated with adjuvant pembrolizumab had tumors with decreased levels of mRNA expression. Conversely the majority (9/14) of patients treated with neoadjuvant pembrolizumab had tumors with increased levels of mRNA expression. Adapted from Cloughesy et. al.

Immune correlative studies will also aid in understanding, which patients respond better to checkpoint inhibition for future studies. For these purposes, blood will be drawn at various time points throughout the study, as outlined in Table 1.

Additionally, a sample of the resected tumor will be requested for correlative analysis if enough tissue is available after standard pathologic testing. We will also request a sample of archival tissue from an extracranial site pretreatment. The full correlative study plan is detailed in Section 12.7.5 and the Correlative Lab Manual (CLM).

#### 9.4. Definition of Evaluable Subjects, On Study, and End of Study

Section 15.2 indirectly addresses the definition of evaluable patients. All eligible patients who initiate checkpoint treatment will be followed for survival regardless of compliance to assigned treatment. In addition, all patients who initiate checkpoint treatment will be included in the denominator for assessing feasibility, whether or not a surgery occurs.

Participants will be considered on study once they have signed the informed consent form and eligibility has been confirmed. The study will be ended once all subjects have completed follow up and all data analysis is complete.

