### **10.2.4. Dispensing and Preparation**

Ipilimumab is given via IV over 90 minutes through an intravenous line containing a sterile, non-pyrogenic, low protein binding in-line filter. The drug product should be visually inspected for particulate matter and discoloration prior to administration and infusion preparation. If the vial of solution appears cloudy, is discolored, or contains foreign particulate matter other than a few translucent-to-white, amorphous particles, it should be discarded [19].

The infusion solution should be prepared as follows [19]:

- Allow the vials to stand at room temperature for approximately 5 minutes prior to preparation of infusion.
- Withdraw the required volume of ipilimumab and transfer into an intravenous bag.
- Dilute with 0.9% Sodium Chloride Injection, USP or 5% Dextrose Injection, USP to prepare a diluted solution with a final concentration ranging from 1 mg/mL to 2 mg/mL. Mix diluted solution by gentle inversion.
- Store the diluted solution for no more than 24 hours under refrigeration (2°C to 8°C, 36°F to 46°F) or at room temperature (20°C to 25°C, 68°F to 77°F).
- Discard partially used vials or empty vials of ipilimumab.

The prepared solution should be administered as follows [19]:

- Do not mix ipilimumab with, or administer as an infusion with, other medicinal products.
- Flush the intravenous line with 0.9% Sodium Chloride Injection, USP or 5% Dextrose Injection, USP after each dose.
- Administer diluted solution over 90 minutes through an intravenous line containing a sterile, non-pyrogenic, low-protein-binding in-line filter.

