### **12.6. Early Withdrawal of Subject(s)**

### **12.6.1. Criteria for Early Withdrawal**

Subjects may voluntarily withdraw from the study at any time. The PI may also withdraw a subject from the study at any time based on his/her discretion. Reasons for PI-initiated withdrawal may include, but is not limited to the following:

- If, in the investigator's medical judgment, further participation would be injurious to the subject's health or wellbeing
- Protocol deviation
- Administrative issues
- Non-compliance of the subject
- Pregnancy
- They do not receive neoadjuvant nivolumab and ipilimumab infusions

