### **12.6.3. Replacement of Early Withdrawal(s)**

Subjects who withdraw from the study without receiving both nivolumab and ipilimumab will be considered non-evaluable; those subjects will be replaced.

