### 15.2. Analysis Sets

The primary analysis associated with the assessment of feasibility, survival, progression-free survival, and time to intracranial progression will include all eligible patients who receive both nivolumab and ipilimumab.

Correlative analyses may be limited to only those patients who provide adequate specimens for analyses.

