#### **15.5.1.2. Continuous Monitoring of Feasibility and Analysis**

The proportion of patients experiencing surgical delay as defined in Section 15.5.1.1 will be computed as the number of patients with delayed surgery or whom never have surgery as a direct or indirect result of ipilimumab and/or nivolumab treatment divided by the total number of patients.

Neoadjuvant treatment patients who have delayed surgery or no surgery due to reasons unrelated to ipilimumab and/or nivolumab treatment will be excluded from the assessment of feasibility. However, this patient will be included in all other analyses if data is available. Reasons for such exclusions will be tabulated. All other patients will be considered evaluable for the assessment of feasibility.

Methods developed for continuous monitoring of toxicity will assess whether the number of surgical delays is not excessive. Based upon the Pocock boundary, the following monitoring rules were developed assuming that a true surgical delay rate of 10% is acceptable, and a surgical delay rate of 20% is too high. Accrual of patients will be suspended if the following conditions are satisfied:

# of Patients Enrolled to Date	Suspend Treatment Assignment if
1 – 4	# Evaluable Patients with Delayed Surgery > 1
5 – 8	# Evaluable Patients with Delayed Surgery > 2
6 – 14	# Evaluable Patients with Delayed Surgery > 3
15+	# Evaluable Patients with Delayed Surgery > 4

These monitoring rules were generated using the R software package. Specifically, the toxbdry function in the clinfun package (<https://cran.r-project.org/web/packages/clinfun/clinfun.pdf>) that implements methods developed by Jennison and Turnbull [20] and Ivanova et al [21] was used.

If accrual is suspended, the reasons for delay will be carefully reviewed to determine whether accrual should continue without any protocol modification, be permanently terminated, or whether modifications to the treatment regimen (e.g., removal of ipilimumab from the treatment regimen) should occur.

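### Feasibility endpoint: Sections 9.4 and 15.5.1.2 keep a one-drug patient with a treatment-related delay, Section 15.2 leaves that patient out, and the suspension-table index and delay clock also need reconciling

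*Combined protocol and SAP*

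**What the plan says.** **Who counts.** Section 9.4 states that "all patients who initiate checkpoint treatment will be included in the denominator for assessing feasibility, whether or not a surgery occurs". The same section also says that "Section 15.2 indirectly addresses the definition of evaluable patients". Section 15.2, which names feasibility, says that the primary analysis "will include all eligible patients who receive both nivolumab and ipilimumab". Section 12.6.1 gives, among possible reasons for withdrawal by the investigator, "They do not receive neoadjuvant nivolumab and ipilimumab infusions". Section 12.6.3 says that subjects who withdraw "without receiving both nivolumab and ipilimumab will be considered non-evaluable; those subjects will be replaced".

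**Unrelated delays.** Section 15.5.1.2 says that patients with delayed or no surgery "due to reasons unrelated to ipilimumab and/or nivolumab treatment will be excluded from the assessment of feasibility", and then declares every other patient evaluable for feasibility. Its numerator is delay or no surgery resulting from either drug or both.

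**Suspension table (15.5.1.2).** The row is chosen by the number of patients enrolled to date; the count is of evaluable patients with delayed surgery. The limits are more than 1 (1–4 enrolled), more than 2 (5–8), more than 3 (row printed as 6–14) and more than 4 (15 or more). A true delay rate of 10% is called acceptable and 20% too high.

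**Clock.** Section 8 calls surgery delayed if it is more than 10 days after the drugs. Sections 5.6 and 15.5.1.1 call it delayed after Day 4, on the premise of infusion on Day -7 and surgery scheduled for Day 1. Section 12.2 and Table 1 allow infusion on Day -10 to Day -4.

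**The concern.** Feasibility is the first primary objective, and surgical delay drives the only numerical suspension rule in the plan. The endpoint exists to detect patients whose surgery is delayed or lost because of the immunotherapy. If one section keeps such a patient and another leaves the patient out, the analyst has to choose, possibly with the outcome already known. One of the two choices makes the treatment look more feasible.

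One-drug dosing is possible on the plan's own text. The infusions are separate: for ipilimumab, Section 10.2.4 says "Do not mix ipilimumab with, or administer as an infusion with, other medicinal products". Section 9.1.3 foresees ipilimumab infusion reactions. The documents do not say how often only one drug would be given.

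The enrolled/evaluable mismatch, the handling of unrelated delays and the clock raise the same issue on a smaller scale: the same facts can give different counts depending on the section followed.

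**Working it through.** **1. The plan's own limits.** Take a constant nominal level against a 10% delay rate, and for each n find the smallest r with P(X ≥ r | n, 0.10) at or below that level.
- n = 4: P(X ≥ 2) = 1 − 0.9⁴ − 4 × 0.1 × 0.9³ = 1 − 0.6561 − 0.2916 = 0.0523.
- n = 5: P(X ≥ 2) = 1 − 0.9⁵ − 5 × 0.1 × 0.9⁴ = 1 − 0.5905 − 0.3281 = 0.0815 (unrounded 0.08146).

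A level of 0.0525 reproduces all four limits if the row printed 6–14 is read as 9–14. An exact patient-by-patient recursion to 20 patients gives a suspension probability of 10.4% at a true rate of 10% and 47.2% at 20%. The plan states no error rates to compare with these. In this calculation, n is the number of patients whose outcomes are counted.

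**2. One drug received, related delay or no surgery.**

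| Section | Treatment of this patient |
|---|---|
| 9.4 | In the denominator (started checkpoint treatment) |
| 15.5.1.2 | Evaluable, and in the numerator (delay due to either drug) |
| 15.2 | Not in the feasibility analysis (both drugs required) |
| 12.6.3 | Non-evaluable and replaced, if the patient withdraws |

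**3. Size (assumed counts: 2 other related delays, one such patient).**
- No replacement, 20 starters: kept, (2 + 1)/20 = 15% (exact 95% CI 3.2–37.9%); left out, 2/(20 − 1) = 10.5% (1.3–33.1%).
- Replaced by an undelayed patient, 21 starters: kept, 3/21 = 14.3% (3.0–36.3%); left out, 2/20 = 10.0% (1.2–31.7%).

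The shift is 4.5 points without replacement (15.0 − 10.5) and 4.3 points with it (14.3 − 10.0), well inside either interval.

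**4. Row of the suspension table.** Suppose 5 are enrolled, 1 is excluded for an unrelated delay, and 2 of the remaining 4 have related delays. By enrolment (row 5–8) the limit is more than 2, so accrual continues. By the evaluable set (row 1–4) the limit is more than 1, so accrual is suspended. Two delays among 4 have tail probability 0.0523, inside the level; two among 5 have 0.0815, outside it.

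**5. Unrelated delays (assumed: 20 starters, 2 related delays, 1 unrelated, no one-drug patients).** Kept, as in 9.4: 2/20 = 10.0%. Excluded, as in 15.5.1.2: 2/19 = 10.5%. All-cause over all starters: 3/20 = 15%. Exclusion raises the related rate slightly.

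**6. Clock.** With no Day 0, the days from infusion day I (negative) to surgery day S (positive) are S − I − 1. Section 8 is met when S − I − 1 ≤ 10, that is S ≤ I + 11. For I = -10, -9, -8, -7, -6, -5, -4 the last on-time day is Day 1, 2, 3, 4, 5, 6, 7. Under 15.5.1.1 it is always Day 4. The two agree at I = -7. If Day 1 is the scheduled surgery day, infusion on Day -10 with surgery on Day 2 (11 days) is late only under Section 8; infusion on Day -4 with surgery on Day 5 (8 days) is late only under 15.5.1.1.

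**The case against.** The strongest answer is that Section 15.5.1.2, the specific rule and the home of the suspension table, already settles the main case. It excludes only unrelated delays, calls everyone else evaluable, and counts delays due to either drug. A reader might infer from 15.2 and 12.6.3 that a one-drug failure necessarily disappears from the suspension count. The documents do not support that: it happens only if 15.2 or 12.6.3 is taken to override 15.5.1.2. This stands, and the conflict is therefore 9.4 and 15.5.1.2 on one side against 15.2 and 12.6.3 on the other.

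The route to one-drug dosing is also narrow. Section 9.1.3 says "If an infusion reaction occurs, the infusion will be slowed or stopped until the symptoms have been treated", which describes a pause, not an omitted drug, and 15.2 does not ask for a full dose. Both infusions are listed at one visit. Replacement further requires withdrawal, and the 12.6.1 reasons are discretionary. This stands as an argument about frequency; it does not remove the contradiction.

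On the clock, a reader might infer that patients infused on any day other than Day -7 will be misclassified. That does not follow. If days are numbered from an infusion called Day -7 the clocks agree, Table 1 calls its days approximate, and infusion on Day -10 with surgery on Day 2 to 4 is 11 to 13 days, already beyond the upper end of 7 ± 3 days. The point is a conditional ambiguity.

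Nor does Section 5.6 set up a competing any-cause endpoint: it refers to 15.5.1.1, which ties the feasibility proportion to the treatment.

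Finally, 15.4 reports surgery timing in the flow diagram and 15.5.1.2 tabulates reasons for exclusion. That helps transparency but does not define the primary rate.

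**Conclusion.** The concern holds. The feasibility set is contradictory for a patient who received one drug and had a treatment-related delay, and following 15.2 and 12.6.3 would remove a treatment-caused failure in the favourable direction. On the assumed counts, one such patient moves the rate by between 4 and 5 points; the number who will occur is unknown and probably small.

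The suspension-table mismatch is separate and needs no one-drug patient: a single exclusion for an unrelated delay can move the study to a looser row. The conflict over unrelated delays is real but small, and either rule has a cost. The clock conflict arises only if Day 1 is fixed as the scheduled surgery day and infusion falls on another permitted day.

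A reader might go further and infer that the trial could wrongly be declared feasible. The plan does not support that: it states no final feasibility threshold, and suspension leads to review, which may end in continuing without change. The matter should be fixed, but its consequence is limited.

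**What to change.** 1. Amend 15.2 and 12.6.3 so that every patient who starts either drug stays in the feasibility set and in the suspension count, in line with 9.4 and 15.5.1.2, even if another patient is added for Ki67.
2. Choose the suspension-table row by the same evaluable set that supplies the count of delays, and correct the overlapping row labels (5–8 and 6–14).
3. Reconcile 9.4 and 15.5.1.2 to one stated rule for unrelated delays. Keeping these patients counts them as non-failures and lowers the rate; excluding them makes the set depend on attribution made after the outcome. Whichever is chosen, report all-cause delay or no surgery over all starters beside the treatment-related rate.
4. Use one endpoint clock in 5.6, 8 and 15.5.1.1, counted from the actual infusion date. This concerns endpoint classification only; the infusion and surgery windows are unchanged.

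The cost is wording in the protocol and its statistical section, one extra reported rate, and keeping infusion date, surgery date and reason for delay for every starter. The reported rate may be slightly less favourable. The 20-patient sample size is unaffected, since its justification in 15.8 rests on Ki67.
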